9.3 INTERIM ANALYSES

We plan to conduct 1 fixed pre-scheduled interim analyses for futility as per the Simon's design as described in section 9.2. The interim analysis will be conducted after follow-up data from the first 14 patients will be available after at least 30 days from study inclusion, or otherwise presenting an occurrence of the primary outcomes. The DSMB will consist of 3 members (2 hepatologists and 1 nurse) and an agreed charter by all members will come into operation before the initiation of the study recruitment. To note, this interim futility analysis will have no impact on the type I error at the end of the trial, and thus alpha adjustment is not needed.

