Follow-up will include clinical and laboratory assessment every 2 weeks within the first 2 month, then every 4 weeks, tumor evaluation at week 4 and every 8 weeks thereafter. In addition, unscheduled visits will be made should they be needed (adverse events or symptoms). At each time point that the dose is changed we will perform a blood extraction to determine serum biomarkers. Moreover, a second extraction will be done 7 days after modifying the cabozantinib dose. Adverse events will be graded following version 5.0 of the CTCAE of the National Cancer Institute, during treatment and 30 days after the last dose. Tumor evaluation during follow-up will be evaluated by CT-scan. Response and TP will be defined according to the RECIST criteria v1.1. Outcomes will be measured from the date of starting cabozantinib until the date of death regardless of cause of death. TTP will be defined as the time from the starting date of cabozantinib to disease progression (according to RECISTv1.1). PPS will be measured from the date of detecting progression at radiology until the date of death or

last follow-up. Assessment will be done by radiologists in each center and then a central revision by radiologists with more than 10 years of experience in HCC and blinded to the evolution and outcome of the patients. Disease-control rate (DCR) will be defined as the percentage of patients who had a best-response rating of complete response (CR), partial response (PR) or stable disease (SD) (according to RECIST and BCLC-RECIST) maintained for at least 28 days after the first demonstration of best-response rating as per independent radiologic review.

Statistical & Analytical Plan and Methodology

The study will be analyzed using standard statistical methods to estimate rates and 95%CI (for ORR and other binary variables) by means of the Clopper-Pearson exact method, and the Kaplan-Meier method to describe the survival functions and the median and [95%CI]. A Statistical Analysis Plan, which will include all details regarding all analyses, the interim method, the handling of missing data and any plan for the analysis, will be finalized before the initiation of the study recruitment.

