6.1.4.2 GENERAL

The side effect profile of cabozantinib includes GI symptoms (such as nausea, vomiting, and diarrhea, mucositis/stomatitis), fatigue/asthenia, anorexia, weight loss, skin disorders including PPE syndrome, elevated liver function tests (including alanine aminotransferase [ALT] and AST), increased pancreatic enzymes with rare cases of overt pancreatitis, hypothyroidism, QTc prolongation, as well as side effects associated with inhibition of VEGF signaling. The latter of these include arterial and venous thrombotic events such as deep vein thrombosis (DVT), pulmonary embolism (PE), transient ischemic attack, and myocardial infarction; hypertension; hemorrhagic events; proteinuria, wound complications, and rare cases of GI perforation, fistulae formation and rectal/perirectal abscess, osteonecrosis, and reversible posterior leukoencephalopathy (RPLS). Please refer to the Investigator's Brochure for additional details. As with all investigational products, unknown AEs may occur. Subjects should be monitored closely throughout their study participation for all AEs. As with other agents in development, additional AEs are unknown. As of 22 October 2013, in studies with cabozantinib,

angioedema has been reported to occur in ~0.1% of subjects treated. The predicted effective plasma half-life of cabozantinib is 55 hours. Thus, when initiating therapy with cabozantinib, it will take most subjects 2-3 weeks to reach steady state after daily dosing. If AEs attributable to cabozantinib occur within the initial 3-week period of dosing, early intervention with dose modifications may be justified for AEs that, if worsened, could potentially be dangerous or debilitating, since without a dose adjustment, systemic exposure of cabozantinib might be expected to increase after the onset of the AE. Management of fatigue, anorexia, diarrhea, nausea, skin disorders, vomiting, rash, hypertension, proteinuria, elevated ALT and AST, myelosuppression, mucositis, hypothyroidism, and cardiac disorders are presented in this section as these have been observed in previous studies with cabozantinib or represent common class effect toxicity. In addition, guidelines to minimize the risk for potential SAEs such as GI and non-GI perforation and fistula formation, hemorrhagic events, and osteonecrosis of the jaw (ONJ) are provided in this section. Please refer to the Investigator's Brochure for additional practice guidelines and management

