9. STATISTICAL METHODS

9.1 END-POINTS

The study will be analyzed using standard statistical methods to estimate rates and 95%CI (for ORR and other binary variables) by means of the Clopper-Pearson exact method, and the Kaplan-Meier method to describe the survival functions and the median and [95%CI]. Indirect comparisons with will conducted with external data by assessing the 95%CI of the study estimates. A Statistical Analysis Plan, which will include all details regarding all analyses, the interim method, the handling of missing data and any plan for the analysis, will be finalized before the initiation of the study recruitment.

Primary Outcome(s)

- Rate of adverse events (AE) with Common Terminology Criteria for Adverse Events (CTCAE)≥3 excluding palmar-plantar erythrodysthesia, rate of AEs, rate of related-AEs and rate of death. Rate of AEs leading to treatment discontinuation.
- Adverse events will be graded following version 5.0 of the CTCAE of the National Cancer Institute, during treatment and 30 days after the last dose.

Secondary Outcome(s)

Time to progression, objective response rate, pattern of progression, overall survival, post-progression survival, rate of patients who develop new extrahepatic spread. Serum and tissue marker characterization.

Safety Outcomes

This is a clinical trial were the main purpose is the assessment of safety, therefore, the primary and secondary outcomes were defined accordingly, as described above.

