9.2 SAMPLE SIZE

The sample size calculation will be triggered by the primary outcome, i.e, the rate of adverse events (AE) with CTCAE \geq 3 excluding palmar-plantar erythrodysthesia (critical AEs). The expected rate for this outcome was 56% in this population¹. The Simon's two-stage optimal design² will be used to test the alternative hypothesis that with cabozantinib the rate of critical AEs will be reduced at least to 32.5% against the null hypothesis of 56% as previously observed. In the first stage, 14 patients will be accrued. If there are 8 or more critical AEs in these 14 patients, the study will be stopped because of futility. Otherwise, 26 additional patients will be accrued for a total of 40. The null hypothesis will be rejected if 23 or fewer critical AEs are observed in 40 patients. This design yields a type I error rate of 2.5% one-sided and power of 80% when the true response rate is 67.5%.

All patients exposed to the study treatment (regardless of protocol adherence) will count be safety, and thus no need to sample size increases as per potential withdrawals are foreseen.

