7.5 INTERIM ANALYSES

We plan to conduct 1 fixed pre-scheduled interim analyses for futility as per the Simon's design as described in section 7.4. The interim analysis will be conducted after follow-up data from the first 14 patients will be available after at least 30 days from study inclusion, or otherwise presenting an occurrence of the primary outcomes. The DSMB will consist of 3 members (2 hepatologists and 1 nurse) and an agreed charter by all members will come into operation before the initiation of the study recruitment. To note, this interim futility analysis will have no impact on the type I error at the end of the trial, and thus alpha adjustment is not needed.

The interim analyses will be performed by a statistician of the Medical Statistics core facility independent to the trial design, conduct of the trial and final analysis.

A previous Data Review will be performed before lock of database for the interim analysis. Data Review Meeting with the sponsor in order to carry out the valid population to the interim analysis (according with section 7.4 and 7.5 specifications).

The interim analysis report will be included the conclusions for the observed data according to the stopping roles in section 7.4 and complete list of adverse events characteristics by subject.

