8.3.2 Secondary outcomes

ORR will be the first relevant ranked secondary outcome:

- Defined as a partial or complete response at any time, i.e. the best response from inclusion along all follow-up.

The rest of secondary end points are:

1. Time to progression (TTP): time to the first progression, defined as the time from the inclusion date to progression (i.e. date of progression event or censoring – date of inclusion + 1).
2. Pattern of progression:
 - Intrahepatic growth (IHG): increased size of intrahepatic target lesions or progression of intrahepatic "non-target" lesions at baseline.
 - New intrahepatic lesion (NIH): emergence of new intrahepatic lesions
 - Extrahepatic growth (EHG): increased size of extrahepatic target lesions, progression of extrahepatic "non-target" lesions at baseline or progression of the existing vascular invasion.
3. Rate of patients who develop new extra-hepatic spread

4. Overall survival (OS): defined as the time from the inclusion date to death from any cause (i.e. date of death event or censoring – date of inclusion + 1).
5. Post-progression survival (PPS), for those patients who progressed, the time from the progression date to death from any cause (i.e. date of death event or censoring – date of 1st progression + 1).

Please see description of the censoring rules for time to event variables in section 8.5.1.

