8.6.3 Definitions and derivation of data

The following definitions and derivations will be used for this study:

- The analyses will be performed by visits and the baseline values for the calculation of the differences (absolute or relative) with respect to the baseline using the following strategy:
 - Baseline values will be defined as the last measurement taken before the first administration.

- The value of the baseline visit in case of measurement existing in that visit.
- The value of the screening visit if there is no measurement in the baseline visit.
- Start of the treatment period will be defined as the date of inclusion
- Absolute differences from baseline for each visit:
 - Absolute differences = observed value - baseline value
- Relative differences from baseline (only for the size or tumour):
 - Relative difference = [observed value-baseline value] / baseline value

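### The stage-1 futility count may be taken after as little as 30 days, before the critical-AE endpoint is complete, so the stop rule leans towards continuing by an amount the documents cannot fix

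*Protocol*

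**What the plan says.** Protocol 9.3 and SAP 7.5 plan one futility analysis, taken "after follow-up data from the first 14 patients will be available after at least 30 days from study inclusion". Both sections then let a patient be counted sooner under a second condition: "or otherwise presenting an occurrence of the primary outcomes". The rule it applies is in Protocol 9.2 and SAP 7.4: "If there are 8 or more critical AEs in these 14 patients, the study will be stopped because of futility". A critical AE is there a CTCAE grade 3 or higher event other than palmar-plantar erythrodysesthesia.

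Protocol 9.1 and SAP 8.3.1 collect the primary outcomes "during treatment and 30 days after the last dose". They list several: critical AEs, AEs of any kind, related AEs, deaths, and AEs leading to discontinuation.

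The interim sections do not say what *inclusion* is. SAP 8.6.3 has "Start of the treatment period will be defined as the date of inclusion". SAP 8.3.2 has time to progression "defined as the time from the inclusion date to progression", while the protocol synopsis says "TTP will be defined as the time from the starting date of cabozantinib to disease progression".

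Protocol 9.3 adds that the futility look has no effect on the type I error, so that no alpha adjustment is needed.

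**The concern.** The count and the endpoint cover different periods. A patient on treatment at day 30 has an open endpoint window. Any critical AE still to come is missing from the stage-1 count, and nothing offsets it, so the error has one direction. For the newest patient, Protocol 6.1.4.2 says "it will take most subjects 2-3 weeks to reach steady state after daily dosing"; 30 days on drug is then only 30 − 21 = 9 to 30 − 14 = 16 days at steady state.

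The early trigger is also loose. Read with Protocol 9.1, an occurrence of the primary outcomes can be any AE. A patient with one mild event in the first week could be treated as ready for the count, although the boundary counts critical AEs only.

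This is the only numerical stop for critical AEs in these documents. The DSMB's periodic reviews (Protocol 10.2) have no boundary here, and its charter is a separate document. A count taken too early could let a trial continue that the rule was meant to stop.

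**Working it through.** **The plan's own design.** Take no critical AE as the response, with p0 = 0.44 and p1 = 0.675. The optimal Simon design for a one-sided 2.5% cap and 80% power is then 7/14 and 23/40. This reproduces the plan's 14 and 40, with power 80.04% and attained type I error 2.39%. In critical AEs it means stop at 7 or more of 14 and reject at 16 or fewer of 40. The written limits (8 or more; 23 or fewer) do not give the stated error rates. That is a separate matter. The stop probabilities below use the written rule of 8 or more.

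**Complete follow-up.** P(Bin(14, 0.56) ≥ 8) = 57.6%. P(Bin(14, 0.80) ≥ 8) = 98.8%.

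**Count at the 30-day floor.** Inputs:
- Accrual, from the synopsis timelines: 3 per month as stated (one patient every s = 10 days), or 40 patients over the 28 months from March 2020 to July 2022 = 1.43 per month (30.4 / 1.43, s ≈ 21 days).
- Time on drug of patient i at the count: t_i = 30 + s(14 − i). The mean is 30 + 6.5s, which is 95 days for s = 10 and about 166 days for s = 21.
- Onset (assumption; the documents give none): exponential with mean m = 15, 30, 60 or 90 days. The share of eventual events already seen is q_i = 1 − exp(−t_i/m).
- Events seen = sum of 14 independent Bernoulli(p·q_i) variables; stop if 8 or more. Each patient counts at most once.

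The average share seen is 0.98/0.91/0.75/0.62 at 3 per month and 0.99/0.95/0.85/0.76 at 1.4 per month.

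| True rate | Accrual per month | m = 15 | m = 30 | m = 60 | m = 90 | Complete |
|---|---|---|---|---|---|---|
| 56% | 3 | 54.3% | 42.0% | 18.0% | 6.5% | 57.6% |
| 56% | 1.4 | 55.5% | 48.8% | 33.1% | 19.9% | 57.6% |
| 80% | 3 | 98.3% | 94.4% | 68.8% | 37.0% | 98.8% |
| 80% | 1.4 | 98.5% | 97.0% | 89.2% | 73.4% | 98.8% |

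**Closing the window.** The exponential curve has no end, but the endpoint does. As an illustration, let every window close at 188 days: the median PFS of 5.2 months quoted in Protocol 1.2.3 (5.2 × 30.4 ≈ 158 days) plus 30. Then q_i = min{1, [1 − exp(−t_i/m)] / [1 − exp(−188/m)]}. For m = 90 and a true rate of 80%, the stop probability becomes 58.8% at 3 per month (from 37.0%) and 88.3% at 1.4 per month (from 73.4%).

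**A 56-day floor.** At a true rate of 56% and 3 per month, the four onset means give 57.0/51.1/30.2/14.6%. For m = 60 the gain is (30.2 − 18.0) / (57.6 − 18.0) = 31% of the loss; for m = 90 it is (14.6 − 6.5) / (57.6 − 6.5) = 16%.

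**Type I error.** For the 7/14 and 16/40 design at 56%, it is 2.39% with the stop followed on complete data and P(Bin(40, 0.56) ≤ 16) = 3.05% with no stop. With the 30-day count it lies between 2.42% and 3.00% over the same onset and accrual grid.

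**The case against.** The strongest reply is that the large losses come from an assumed onset curve. That is right: with mean onset of 15 to 30 days and a true rate of 80%, the 30-day count still stops 94.4–98.5% of the time, and closing the window shrinks the slow-onset losses. It is also fair that 56% is the reference rate rather than an excess, and that the floor concerns one patient of 14. These points limit the size. They do not change the direction.

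Other safeguards exist. SAP 7.5 requires a data review before the interim lock and a full AE listing by subject, and the DSMB meets periodically. None of these sets a numerical boundary. On the trigger, Protocol 9.3 refers back to 9.2, which treats critical AEs as the primary outcome, so the intended meaning can be guessed. Naming the event removes the doubt.

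Two stronger readings are tempting.
- A reader might take *inclusion* to be consent, since Protocol 4.1.1 defines study entry that way and allows 28 days to first dose. That would leave the newest patient 30 − 28 = 2 days on drug. But study entry is a different term, SAP 8.6.3 equates inclusion with the start of treatment, and the two definitions of time to progression agree only on that reading. First dose is the better reading, and no weight is put on the consent scenario.
- A reader might infer that the statement on type I error invalidates the test. It does not. A futility stop lowers the error, Protocol 9.2 makes the stop mandatory, and no upward adjustment is needed. SAP 8.6 also calls the analysis non-inferential.

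**Conclusion.** The point holds as a one-directional weakness of unknown size. Followed as written, the stage-1 count can miss critical AEs and so favours continuing. The loss is small if critical AEs appear within weeks: at 56% and mean onset of 15 days, 54.3–55.5% against 57.6%. It is material only if they take months: at 60 days, 18.0–33.1%. These figures rest on exponential onset, independent patients, even accrual, and a count taken at the 30-day floor; a later count would lose less. The documents do not support saying that the rule is ineffective, only that its operating characteristics at the permitted time are not known.

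The type I error sentence is a minor wording matter. It is literally inaccurate (2.39% with the stop, 3.05% without, for the design that delivers the stated error rates), but its conclusion of no adjustment stands.

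**What to change.** In Protocol 9.3, SAP 7.5 and the DSMB charter:
1. Run the interim clock from the first cabozantinib dose.
2. Replace the early trigger with a critical AE as defined in section 9.2 (SAP 7.4).
3. Take the count when each of the first 14 treated patients has had a critical AE, has reached a longer minimum exposure (for example two 28-day cycles), or has completed the 30-day safety follow-up after stopping. Report exposure at the count and the stop probability over a range of assumed onset.
4. Reword the type I error sentence: the two-stage error already allows for the stage-1 stop, holds if that stop is followed, and receives no further adjustment.

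The endpoint itself need not change. Moving the floor from 30 to 56 days delays the count by up to 26 days. Because enrolment continues during DSMB meetings (Protocol 10.2), about 26 × 1.43 / 30.4 = 1.2 to 26 × 3 / 30.4 = 2.6 more patients would enter before the decision. If onset is slow, this recovers only part of the loss (56% rate, 60-day mean, 3 per month: 18.0% to 30.2%, against 57.6%).

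On the planned March 2020 start, patient 14 would enter 13 × 10 = 130 to 13 × 21 = 273 days after the first, before protocol version 4.0 (15 July 2021). If the look has already been taken, report the exposure at that look and the updated stage-1 count instead.

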10. STUDY CONDUCT CONFIDENTIAL

All other study personnel not included in this section are identified in a separate personnel list (not part of this clinical study protocol) as appropriate. This list will be updated as needed; an abbreviated version with personnel relevant for the centers will be available in each center's investigator site file.

Whenever the term 'investigator' is noted in the protocol text, it may refer to either the principal investigator at the site, or an appropriately qualified, trained and delegated individual of the investigational site.

¹ Abou-Alfa GK, Meyer T, Cheng AL, El-Khoueiry AB, Rimassa L, Ryoo BY, Cicin I, Merle P, Chen Y, Park JW, Blanc JF, Bolondi L, Klümppen HJ, Chan SL, Zagonel V, Pressiani T, Ryu MH, Venook AP, Hessel C, Borgman-Hagey AE, Schwab G, Kelley RK. Cabozantinib in Patients with Advanced and Progressing Hepatocellular Carcinoma. *N Engl J Med.* 2018 Jul 5;379(1):54-63. doi: 10.1056/NEJMoa1717002.

² Simon R. Optimal Two-Stage Designs for Phase II Clinical Trials. *Controlled Clinical Trials* 1989;10: 1-10

The principal investigator of each center must sign the protocol signature sheet before subject recruitment may start at the respective center. Likewise, all protocol amendments/integrated protocols must be signed and dated by the principal investigator before coming into effect at the respective center.

A complete list of all participating centers and their investigators, as well as all required signature documents, will be maintained in the sponsor study file.

The global sponsor of this study is identified on the title page of this protocol. If required by local law, local co-sponsors will be nominated; they will be identified on the respective country-specific signature pages.

10.1 ADHERENCE TO THE PROTOCOL

The study shall be conducted as described in this protocol. The investigators should not implement any deviation or change to the protocol without prior review and documented approval/favorable opinion from the IRB/IEC of an amendment, except where necessary to eliminate an immediate hazard(s) to study subjects. If an amendment substantially alters the study design or increases the potential risk to the subject: (1) the consent form must be revised and submitted to the IRB(s)/IEC(s) for review and approval/favorable opinion; (2) the revised form must be used to obtain consent from subjects currently enrolled in the study if they are affected by the amendment; and (3) the new form must be used to obtain consent from new subjects prior to enrollment. If the revision is an administrative letter, investigators must inform their IRB(s)/IEC(s).

10.2 DATA SAFETY MONITORING BOARD (DSMB)

A Data Safety Monitoring Board will be instituted in order to ensure ongoing safety of study patients with respect to a risk/benefit assessment during periodic data review meetings, review results from planned interim analyses and provide a formal recommendation for continuation/termination of the study and monitor study conduct to ensure the overall integrity of trial is maintained. One formal interim analysis is planned and will be performed as per separate DSMB charter. Recommendation for trial continuation will be guided by monitoring boundaries at formal interim analyses as well as safety evaluations at all safety data reviews (refer to Section for details on interim analyses). The committee will include at least 2 independent hepatologist and one independent nurse. Data review meetings will be held periodically as per separate DSMB charter. Enrollment to the study will continue throughout the scheduled meetings of the DSMB. Decisions on trial termination, amendment or cessation of patient recruitment based on risk/benefit assessments will be made after recommendations from the DSMB have been assessed by the Sponsor.

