The sample size calculation will be triggered by the primary outcome, i.e, the rate of adverse events (AE) with CTCAE≥3 excluding palmar-plantar erythrodysthesia (critical AEs). The expected rate for this outcome was 56% in this population. The Simon's two-stage optimal design will be used to test the alternative hypothesis that with cabozantinib the rate of critical AEs will be reduced at least to 32.5% against the null hypothesis of 56%. In the first stage, 14 patients will be accrued and if there are 8 or more critical AES in these 14 patients, the study will be stopped for futility. Otherwise, 26 additional patients will be accrued for a total of 40. The null hypothesis will be rejected if 23 or fewer critical AEs are observed in 40 patients. This design yields a type I error rate of 2.5% one-sided and power of 80% when the true response rate is 67.5%.

Planned Study Timelines:

1. Enrolment rate (patients per month): 3
2. Planned estimate of treatment(s) duration: **24months**
3. Submission date to health authority/ethics: Jan 2020
4. Start of subject enrolment: March 2020
5. End of Subject enrolment: Jul 2022
6. All patients completed: **Oct 2023**
7. End of Study: Jan 2024
8. Report: **Q2-Q3 2024**
9. Planned publication/presentation: Q1 2025

TABLE OF CONTENTS.

| | |
|--|-----------|
| TITLE PAGE | 1 |
| SYNOPSIS | 2 |
| 1. INTRODUCTION | 13 |
| 1.1 HEPATOCELLULAR CARCINOMA | 13 |
| 1.2 CABOZANTINIB: BACKGROUND | 13 |
| 1.2.1 PHARMACOLOGY AND PHARMACOKINETICS..... | 13 |
| 1.2.2 CABOZANTINIB SAFETY SUMMARY IN PATIENTS WITH HEPATOCELLULAR CARCINOMA..... | 16 |
| 1.2.3 SUMMARY OF CABOZANTINIB CLINICAL ACTIVITY IN HEPATOCELLULAR CARCINOMA..... | 16 |
| 1.2.4 RATIONALE FOR THE CURRENT STUDY | 17 |
| 1.2.4.1 TREATMENT SCHEDULE | 17 |
| 2. STUDY OBJECTIVES..... | 17 |
| 3. ETHICAL CONSIDERATIONS..... | 17 |
| 3.1 GOOD CLINICAL PRACTICE | 17 |
| 3.2 INSTITUTIONAL REVIEW BOARD/INDEPENDENT ETHICS COMMITTEE | 18 |
| 3.3 INFORMED CONSENT..... | 18 |
| 4. STUDY DESIGN AND PLAN | 19 |
| 4.1 TREATMENT PLAN..... | 19 |
| 4.1.1 SCREENING PHASE | 19 |
| 4.1.2 CABOZANTINIB..... | 20 |
| 4.1.3 END OF THE STUDY | 20 |
| 4.1.4 DISCONTINUATION OF CABOZANTINIB..... | 21 |
| 4.1.5 POST STUDY DRUG STUDY FOLLOW-UP..... | 21 |
| 4.1.6 WITHDRAWAL OF CONSENT | 21 |
| 4.1.7 LOST TO FOLLOW-UP | 22 |
| 5. PATIENT POPULATION..... | 22 |
| 5.1 INCLUSION CRITERIA..... | 22 |
| 5.1.1 SIGNED WRITTEN INFORMED CONSENT | 22 |
| 5.1.2 TARGET POPULATION | 22 |

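### Protocol 10.2 keeps enrolment open through scheduled DSMB meetings without exempting the stage-1 interim, although the two-stage design makes patients 15 to 40 conditional on that interim

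*Protocol*

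**What the plan says.** **Design.** Protocol 9.2, repeated in the synopsis and SAP 7.4, sets a Simon optimal two-stage design on critical AEs (grade 3 or higher, palmar-plantar erythrodysaesthesia excluded). "In the first stage, 14 patients will be accrued". Then: "If there are 8 or more critical AEs in these 14 patients, the study will be stopped because of futility". Then: "Otherwise, 26 additional patients will be accrued for a total of 40".

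**Timing of the look.** Protocol 9.3 and SAP 7.5: "The interim analysis will be conducted after follow-up data from the first 14 patients will be available after at least 30 days from study inclusion". The sentence goes on to waive the wait for a patient who has already had a primary-outcome event. SAP 7.5 adds a data review with the sponsor and a database lock for the interim.

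**Who decides, and what happens to accrual.** Protocol 10.2 gives the planned interim to the DSMB and refers to a separate charter for its conduct. It leaves any halt to recruitment until the sponsor has considered the DSMB's recommendation. The same paragraph states: "Enrollment to the study will continue throughout the scheduled meetings of the DSMB".

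**Accrual.** The synopsis timelines give "Enrolment rate (patients per month): 3", with enrolment planned from March 2020 to July 2022.

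**The concern.** Under 9.2, whether patient 15 is recruited depends on the result in the first 14. Under 10.2, read literally, recruitment does not pause while that result is awaited and considered. Protocol 9.3 describes the interim as scheduled in advance, so it can fairly be counted among the DSMB's scheduled meetings.

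The documents label the stage-1 stop as futility, but the endpoint is severe toxicity, so in effect it is a stop for too many critical AEs. It is also the only numerical stopping boundary in the plan. If accrual stays open, some patients start treatment who would not have been enrolled had the rule been applied first. A Simon optimal design is chosen because it keeps expected sample size small when the null is true, and open accrual gives back part of that gain.

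**Working it through.** **1. Reproduce the design.** Inputs from 9.2: "against the null hypothesis of 56% as previously observed"; alternative 32.5%; one-sided 2.5%; power 80%. I assume at most one counted critical AE per patient. An exact binomial search with success defined as no critical AE (p0 = 0.44, p1 = 0.675) returns n1 = 14, N = 40 and cut-offs 7 and 23 on the AE-free scale. Alpha is 2.39%, power is 80.04% and the probability of stopping at stage 1 under the null is 0.766. Expected N under the null is 14 + 26 × (1 − 0.766) = 20.1. This matches the plan's 14 + 26 = 40, and I call it the intended boundary.

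The printed rule applies its limits to AE counts instead. Its stop probability is P(X ≥ 8 of 14 | 0.56) = 0.576, so expected N is 14 + 26 × (1 − 0.576) = 25.0. The mismatch between the intended and printed boundaries is a separate error. Both are carried here so that this point does not depend on how that one is resolved.

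**2. Accrual rate.** The stated rate is 3 per month. The planned dates give 40 patients in 28 months, or 40/28 = 1.43 per month. The two disagree, so I use both.

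**3. Time from patient 14 to the decision.** Only the follow-up of up to 30 days is given; that month alone adds about 1.4 to 3 patients. The data review, lock, DSMB recommendation and sponsor decision have no stated duration. I assume 2 to 3 months in total.

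**4. Over-run and expected N at a 56% rate.** With over-run k = rate × months and stop probability S:

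expected N = 14 + k + (1 − S) × (26 − k), which is the no-over-run value plus k × S.

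| Rate per month | Months | k | Intended (S = 0.766) | Printed (S = 0.576) |
|---|---|---|---|---|
| any | hold at 14 | 0 | 20.1 | 25.0 |
| 1.43 | 2 | 2.9 | 22.3 | 26.7 |
| 1.43 | 3 | 4.3 | 23.4 | 27.5 |
| 3 | 2 | 6 | 24.7 | 28.5 |
| 3 | 3 | 9 | 27.0 | 30.2 |

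The saving against a fixed 40 is S × (26 − k), so the share of the saving lost is k/26 under either boundary. That is 11% to 17% at 1.43 per month (2.9/26 and 4.3/26) and 23% to 35% at 3 per month (6/26 and 9/26).

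**5. Error rates.** If the stage-1 count uses only the first 14 patients and the final count uses 40, over-run patients are simply early stage-2 patients. Type I error and power are unchanged.

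**6. Room for a pause.** At 3 per month, 40/3 = 13.3 months; adding 2 to 3 months gives 15.3 to 16.3, inside the 28-month window. At 1.43 per month the window is already full, and the total becomes 30 to 31 months.

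**The case against.** - **10.2 may mean only the periodic reviews.** The enrolment sentence follows directly on the one about periodic data review meetings, and the formal interim is covered earlier in the paragraph. On that reading 9.2 governs the interim and nothing conflicts. This stands as a possible reading, so a flat contradiction is more than the text supports. What remains is that 10.2 makes no exception and no other section supplies a hold.
- **The charter could set a hold.** This also stands, because the charter is not among the documents. If it does, 10.2 should still be worded to agree with it.
- **The 30-day wait is not always needed.** Patients with an early event count at once, so the wait may be shorter when toxicity is high. For that reason 30 days is treated above as an upper limit on the follow-up step.
- **A reader might infer that this rule is the only safeguard.** Protocol 10.2 also provides for safety reviews and for stopping recruitment on risk/benefit grounds. The stage-1 rule is the only numerical boundary, not the only protection.
- **A reader might infer that over-run patients have no place in the analysis.** Protocol 9.2 counts all exposed patients for safety, and the Safety Set in SAP 8.1 takes all eligible treated patients. The open question is narrower: how they enter the final inference if the boundary has been crossed.
- **The stakes are modest.** SAP 8.5 and 8.6 treat the primary endpoints as non-confirmatory and the analysis as non-inferential, and the trial is capped at 40.

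**Conclusion.** The point holds as an unreconciled gap between Protocol 10.2 and the two-stage rule in 9.2/9.3 and SAP 7.4/7.5. It should be fixed, but it does not invalidate the design. The likely over-run is about 3 to 4 patients at 1.4 per month or 6 to 9 at 3 per month. Expected N at a 56% rate rises from 20.1 to 22.3–27.0 (intended boundary) or from 25.0 to 26.7–30.2 (printed boundary).

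These sizes rest on an assumed 2 to 3 months from patient 14 to the decision and on which of the two planned accrual rates applies. The direction is the same under every combination.

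A reader might infer that open accrual inflates the type I error. It does not, provided the stage-1 rule is applied to the first 14 patients only. The harm is additional exposure before the toxicity decision and the loss of part of the design's saving.

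**What to change.** Reconcile 10.2 with 9.2/9.3 and SAP 7.4/7.5. Suggested wording for 10.2: *Enrolment continues during the periodic DSMB safety reviews. Accrual beyond the 14th patient waits for the DSMB's stage-1 recommendation and the sponsor's decision.* Repeat it in 9.3 and SAP 7.5, and check that the charter agrees.

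If the sponsor prefers to keep accrual open, the plan should instead give a maximum over-run, confirm that the stage-1 count uses the first 14 only, and say how the extra patients enter the final analysis if the boundary is crossed.

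The drafting cost is a sentence or two in each document. The operational cost of a hold is a recruitment pause of roughly 2 to 3 months. The enrolment window absorbs this at 3 per month, but it may have to be extended at about 1.4 per month.
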